8.2.4.1. General Adverse Events Summaries

Summaries of the number and percentage of subjects with AEs and the total number of AEs will be provided by treatment group overall and at the SOC and PT level for the following time periods:

- 1) On-therapy and post-therapy combined period
- 2) Pre-therapy (includes hypoglycemia events)
- 3) On-therapy
- 4) Post-therapy

In addition, on-therapy Adverse events will be presented by time intervals of onset (≤ 12 weeks, $>12 - \leq 26$ weeks) and by treatment group; the on-therapy non-serious AEs will be summarized by treatment group.

An additional on-therapy AE summary will also be provided following government clinical register format; these summaries will include the AEs of hypoglycemia event.

A by-subject listing of all AEs will also be presented.

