6.6. Treatment Compliance

Study treatment (both active drug and placebo injector) will be administered to the subject by the site personnel in the clinic at each scheduled weekly visit from Week 0 (i.e. Baseline/Randomization), Week 1 through Week 25. At each scheduled weekly visit, study treatment administration status (Yes/No), date/time of dose administered (if Yes) and reason no dose administered (if No) will be recorded in the Exposure eCRF page.

Treatment compliance (in percentage) will be based on the Exposure eCRF page and calculated as total number of doses administered divided by total number of doses expected over all available scheduled visits on treatment. Treatment compliance will be summarized for all subjects, as well as for subjects who discontinue study treatment early and subjects who complete study treatment. Treatment compliance will be also categorized as < 80% and \geq 80%, and summarized descriptively by treatment group.

Individual subject compliance information will also be listed. All summaries will be performed using the safety population.

Acceptable overall compliance for IP (albiglutide liquid and lyophilized) in this study will be \geq 80%.

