11.3. Appendix 3: Assessment Windows

11.3.1. Definitions of Baseline and Study Day

In general, the baseline value for each variable will be defined as the last measurement collected prior to the first dose of randomized study medication.

Study day will be defined as the number of days from the first dose of randomized study medication. The date when a subject receives the first dose of randomized study medication is defined as Day 1. For events after the first dose date, study day is calculated as the difference in days between the first dose date and the date of interest, plus 1 day. For events that occur before the first dose date, study day is calculated as the difference in days between the first dose date and the date of interest. Thus, the day before first dose date is defined as Day -1.

Note that the date of first dose is Day 1 and the day before the date of first dose is Day -1 (there is no Day 0).

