
* Week 26 is the end of treatment visit for those subjects completing the study per-protocol. For subjects who withdraw early from study treatment, the end of treatment visit will be assigned to an analysis visit based on the visit slotting algorithm using study day and therapy phase.
 
** Week 34 is the 8 week post-treatment follow-up visit for those subjects completing the study per-protocol. The 8 Week Follow-up Visit is the 8 week post-treatment follow-up visit for those subjects who withdraw early from study treatment. Both visits will be assigned based on the visit slotting algorithm using therapy phase.
 
*** The target study day for the 8 Week Follow-up Visit for subjects who withdraw early from study treatment is set to be 9 weeks (63 days) after last dose to correspond with the timing of the 8 week post-treatment follow-up for subjects completing the study per-protocol (where last dose is at Week 25 and the follow-up visit is at Week 34).
		

For lab assessments:

Scheduled Visit	Target Study Day of Visit	Slotting Intervals
Pre-therapy		
Week -2	-14	Not applicable
On-therapy		
Week 1	8	2 to 18 days
Week 4	29	19 to 43 days
Week 8	57	44 to 85 days
Week 16	113	86 to 148 days

Scheduled Visit	Target Study Day of Visit	Slotting Intervals
Week 26 (End of Treatment Visit)*	183	149 to (last dose date + 25 days)
Post-therapy		
Week 34**	239	>Last dose date + 25 days
8 Week Follow-up Visit**	Last dose date + 63 days***	>Last dose date + 25 days

* Week 26 is the end of treatment visit for those subjects completing the study per-protocol. For subjects who withdraw early from study treatment, the end of treatment visit will be assigned to an analysis visit based on the visit slotting algorithm using study day and therapy phase.
 
** Week 34 is the 8 week post-treatment follow-up visit for those subjects completing the study per-protocol. The 8 Week Follow-up Visit is the 8 week post-treatment follow-up visit for those subjects who withdraw early from study treatment. Both visits will be assigned based on the visit slotting algorithm using therapy phase.
 
*** The target study day for the 8 Week Follow-up Visit for subjects who withdraw early from study treatment is set to be 9 weeks (63 days) after last dose to correspond with the timing of the 8 week post-treatment follow-up for subjects completing the study per-protocol (where last dose is at Week 25 and the follow-up visit is at Week 34).
		

For immunogenicity assessments:

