11.4. Appendix 4: Treatment Periods

For classifying AEs (including hypoglycemic events), the therapy periods will be defined as:

- **Pre-therapy:** The onset date of the AE is before the start date of randomized study medication. If the onset date of the AE is on the start date of randomized study medication, the AE will be considered as on-therapy.
- **On-therapy:** The onset date of the AE is on or after the start date of randomized study medication and within 25 days after the date of last dose.
- **Post-therapy:** The onset date of the AE is more than 25 days after the last date of randomized study medication.

For immunogenicity data and other safety parameters that are assessed prior to administration of randomized study medication on dosing days, the therapy periods will be defined as:

- **Pre-therapy:** The assessment date is on or before the start date of randomized study medication.
- **On-therapy:** The assessment date is after the start date of randomized study medication and within 25 days after the date of last dose.
- **Post-therapy:** The assessment date is more than 25 days after the last date of randomized study medication.

For an AE with an incomplete start date where the year and month are present while the day is missing, or where the year is present while both month and day are missing, the date is imputed in a dynamic way consistent with the partial date information so that the resulting AE therapy period assignment based on the imputed date is the most conservative possible, where the order from the most to the least conservative is: on-therapy phase > post-therapy phase > pre-therapy. Note that if the AE stop date is present, then the imputed start date will always be on or prior to the stop date.

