11.14.5. Safety Tables

Safety : Tables					
No.	Population	IDSL / TST ID / Example Shell	Title	Programming Notes	Deliverable [Priority]
Exposure and Compliance					
3.1.	Safety		Exposure to Treatment		
3.2.	Safety		Treatment Compliance		
[Adverse Events]					
3.11.	Safety		Overview of Adverse Events		
3.12.	Safety		All On-therapy and Post-therapy Adverse Events		
3.13.	Safety		Pre-therapy Adverse Events		
3.14.	Safety		On-therapy Adverse Events		
3.15.	Safety		Most Common On-therapy Adverse Events		
3.16.	Safety		Post-therapy Adverse Events		
3.17.	Safety		On-Therapy Adverse Events and the Information on Relation to Treatment		
3.18.	Safety		On-therapy Adverse Events by Time of Onset with 12-Weeks Intervals		
3.19.	Safety		On-therapy Non-serious Adverse Events		
3.20.	Safety		On-Therapy Non-serious Adverse Events with Incidence of Preferred Term >2% in Any Treatment Group and the Information on Relation to Treatment		
3.21.	Safety		On-therapy and Post-therapy Adverse Events Related to Study Treatment		
3.22.	Safety		On-therapy Treatment-related Adverse Events		
3.23.	Safety		Post-therapy Treatment-related Adverse Events		

Safety : Tables					
No.	Population	IDSL / TST ID / Example Shell	Title	Programming Notes	Deliverable [Priority]
3.24.	Safety		On-therapy and Post-therapy Treatment-related Adverse Events		
3.31.	Safety		Overall Summary of On-therapy and Post-therapy Adverse Events by Maximum Intensity		
3.32.	Safety		On-therapy Adverse Events by Maximum Intensity		
3.33.	Safety		Post-therapy Adverse Events by Maximum Intensity		
3.34.	Safety		On-therapy and Post-therapy Adverse Events by Maximum Intensity		
3.41.	Safety		Pre-therapy Serious Adverse Events		
3.42.	Safety		On-therapy Serious Adverse Events		
3.43.	Safety		On-Therapy Serious Adverse Events and the Information on Relation to Treatment		
3.44.	Safety		Post-therapy Serious Adverse Events		
3.45.	Safety		On-therapy Treatment-related Serious Adverse Events		
3.46.	Safety		Post-therapy Treatment-related Serious Adverse Events		
3.47.	Safety		On-Therapy Fatal Serious Adverse Events and the Information on Relation to Treatment		
3.48.	Safety		On-Therapy Non-fatal Serious Adverse Events and the Information on Relation to Treatment		
3.51.	Safety		On-therapy Adverse Events Leading to Permanent Discontinuation of Study Treatment		
3.52.	Safety		On-therapy Adverse Events Leading to Withdrawal from Study		
Adverse Events of Special Interest					

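### The table of on-therapy AEs by onset interval stops at 26 weeks, but the on-therapy period runs to 25 days after the last dose, so roughly its last two to three weeks have no column

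*SAP*

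**What the plan says.** - SAP 8.2.4.1 (general AE summaries): "on-therapy Adverse events will be presented by time intervals of onset". Two intervals follow, up to and including 12 weeks, and over 12 up to and including 26 weeks. There is no later or open-ended interval.
- SAP 11.4 (Appendix 4): an AE is on-therapy if its onset is on or after the first dose and "within 25 days after the date of last dose". It becomes post-therapy only when "The onset date of the AE is more than 25 days after the last date of randomized study medication".
- SAP 6.6: doses are scheduled "from Week 0 (i.e. Baseline/Randomization), Week 1 through Week 25". The footnotes to the visit windows in SAP 11.3.4 confirm this for completers: "where last dose is at Week 25 and the follow-up visit is at Week 34".
- SAP 11.3.1: "The date when a subject receives the first dose of randomized study medication is defined as Day 1".
- SAP 11.14.5 lists the display as Table 3.18, titled "On-therapy Adverse Events by Time of Onset with 12-Weeks Intervals". The shell and programming-note cells are empty.
- Protocol 7.4.1.1: AEs are collected until the follow-up contact, so events after Week 26 will be in the database.

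**The concern.** The table is restricted to on-therapy AEs and split by onset time, so its columns should together cover the on-therapy period. As specified they do not. An AE that starts after 26 weeks but within 25 days of the last dose is on-therapy by Appendix 4 and belongs in Table 3.14, yet it has no place in Table 3.18.

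The rest of the SAP treats those days as on-therapy. Total person time (Appendix 5) is extended past the last dose because of the long half-life, and event-free subjects in the time-to-first-event analyses are censored at last dose + 25 days. Protocol 6.9 says therapeutic levels may last three to four weeks after stopping. The onset-interval table is the exception.

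What is at stake is limited. Event counts in the two columns may not add up to the on-therapy total, and a reader could not tell a programming error from an intended exclusion. The title adds to the doubt. The first interval is 12 weeks long, but the second is 26 − 12 = 14 weeks, so the text and the title give the programmer two different specifications.

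**Working it through.** **Inputs.** First dose = Day 1 (SAP 11.3.1), so Week w has target Day 7w + 1. Last scheduled dose is at Week 25 (SAP 6.6 and 11.3.4). On-therapy ends at last dose + 25 days (Appendix 4). The visit window is ±3 days (Protocol section 7).

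**Reproducing the SAP's own days.** Week 25 = 7 × 25 + 1 = Day 176. Week 26 = 7 × 26 + 1 = Day 183. Week 34 = 7 × 34 + 1 = Day 239. The SAP places the post-treatment follow-up 63 days after the last dose: 176 + 63 = 239, which agrees.

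**End of on-therapy.** 176 + 25 = Day 201. Appendix 5 gives the same length for person time: (176 − 1) + 26 = 201 days.

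**Where 26 weeks ends.** The SAP gives no week-to-day rule for AE onset. Counting 26 × 7 days, the second interval closes on Day 182. Counting elapsed time from Day 1, it closes on Day 183, the SAP's Week 26 target day. The same one-day doubt applies at 12 weeks (Day 84 or Day 85).

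**Days with no column:**

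| Last dose | On-therapy ends | Gap if 26 weeks = Day 182 | Gap if 26 weeks = Day 183 |
|---|---|---|---|
| Week 25, 3 days early (Day 173) | Day 198 | 16 days | 15 days |
| Week 25, on target (Day 176) | Day 201 | 19 days | 18 days |
| Week 25, 3 days late (Day 179) | Day 204 | 22 days | 21 days |
| Week 24, on target (Day 169) | Day 194 | 12 days | 11 days |
| Week 23, on target (Day 162) | Day 187 | 5 days | 4 days |
| Week 22, on target (Day 155) | Day 180 | none | none |

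Check at the target day with the Day 182 convention: 84 days (up to 12 weeks) + 98 days (over 12 to 26 weeks) + 19 days = 201.

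As a share of the on-therapy window at the target day, 19/201 = 9.5%, or 18/201 = 9.0%. These are shares of calendar time. The documents give no late-onset AE rate, so they are not shares of events.

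**Does another rule close the gap?** In several SAP 11.3.4 tables (vital signs, ECG, laboratory, immunogenicity, weight) the Week 26 slot runs to last dose + 25 days. SAP 11.3.2 limits that slotting to parameters summarized or analyzed by visit. AE onset is not one of these, and nothing comparable is stated for onset intervals.

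**The case against.** Four points on the other side deserve weight.

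1. **No event is lost.** A reader might infer that late events, including immune-related ones, vanish from the report. The documents do not support that. Every affected AE stays in Table 3.14, the combined on- and post-therapy table (3.12) and Listing 136. Injection site reactions have a by-week display and a Kaplan-Meier analysis (Tables 3.143 and 3.142). Systemic allergic reactions have Kaplan-Meier analyses (3.133 and 3.134). These Kaplan-Meier analyses follow the GI method, with censoring at last dose + 25 days. GI events are shown by onset week (3.117). So are hypoglycemic events (3.80), which most general AE summaries exclude anyway. This objection stands and confines the point to the all-AE onset table.

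2. **The layout of Table 3.18 is inferred.** There is no shell, and literal 12-week bins, as in the title, would continue past Week 24 and could capture these events. That is fair. But the text states two closed intervals, so either the text leaves events out or the title overrides it, and the two have to be reconciled in any case.

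3. **The size is uncertain.** A reader might infer that subjects who enter the extension contribute no gap because their Week 26 visit is Visit 1 of Study 204682. Appendix 4 does not cut on-therapy off at extension entry, and the SAP does not say in which study their later AEs count. SAP 8.2.1 says only that their safety and exposure will also be summarized. The affected share is therefore unknown.

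4. **Nothing inferential depends on it.** Protocol 9.4.2 plans no inferential testing of safety variables. This stands and keeps the point minor.

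**Conclusion.** The inconsistency is real: two stated SAP rules together produce a table that does not cover the period it is defined on. At the target dosing day 19 on-therapy days have no column, or 18 if Day 183 counts as 26 weeks. Across the ±3-day window the gap is 16 to 22 days (15 to 21 under the Day 183 convention). Subjects whose last dose is at Week 23 or 24 are affected for fewer days.

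This rests on reading the two intervals in SAP 8.2.4.1 literally and on the last scheduled dose being at Week 25. How many subjects and events it touches cannot be derived from the documents. The effect is confined to Table 3.18 and its reconciliation with the on-therapy total. No endpoint, hypothesis or listing is affected. It is worth correcting before unblinding, but it is a tidying point.

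**What to change.** - In SAP 8.2.4.1 add a third column running from after 26 weeks to the end of on-therapy (last dose + 25 days).
- State the week-to-day rule for AE onset, which settles both the 12-week and the 26-week boundary.
- State how AEs after the Week 26 visit are counted for subjects who enter Study 204682.
- Retitle Table 3.18 to match the intervals in the text.

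A separate column is better than making the over-12-weeks interval open-ended, which would mix the dosing period with the post-dose period. With three columns, the numbers of events add up to the on-therapy total. Subject counts need not, because one subject can have events in more than one interval.

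The cost is a few lines of SAP text and a table title. No new data are needed. The third column may be sparse.

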8.2.4.2. Treatment Emergent Adverse Events

TEAEs are defined as any AEs, regardless of relationship to the, randomized study drug (i.e., albiglutide or other study treatments), that occur after the first dose of the randomized study medication, which is equivalent to on-therapy and post-therapy AEs combined. Summaries of the number and percentage of subjects with TEAEs will be provided by treatment group overall at the SOC and PT level. TEAEs will also be further defined as on-therapy or post-therapy AEs for summary purposes.

A by-subject listing of all TEAEs will also be presented.

8.2.4.3. Treatment-Related Adverse Events

Treatment-related AEs will be defined as any AEs that are considered by the investigator to have a reasonable possibility to be related to the study treatment. If a relationship to the study treatment is missing or unknown after the start of treatment it will be assumed, for the purpose of analyses, to be treatment-related.

A summary of the number and percentage of subjects with treatment-related AEs will be displayed. The treatment-related AE data will be categorized and presented in a manner similar to that described above for the general AE summaries for both the on-therapy and post-therapy therapeutic phases.

8.2.4.4. Adverse Events by Maximum Intensity

A summary of the number and percentage of subjects with on-therapy and post-therapy adverse events by intensity (mild, moderate, and severe) will be produced. The data will be sorted and categorized using the method and format described previously.

Subjects who experience the same event several times with different intensity will only be counted once according to the maximum intensity experienced (for that therapeutic phase).

8.2.4.5. Most Common Adverse Events

A summary of most common on-therapy adverse events (>2% total incidence in any treatment arm) by treatment will be produced.

In addition, on-therapy non-serious AEs with proportion of subjects experiencing the AE $\geq 5\%$ among any of the active arms will be summarized by treatment group following government clinical register format; this summary will include AEs of hypoglycemia event.

8.2.5. Deaths and Serious Adverse Events

Serious adverse events (SAEs) will be summarized in a manner similar to that described above for the general AE summaries by treatment group for pre-therapy, on-therapy, and post-therapy therapeutic phases. Treatment-related SAEs will also be summarized separately by treatment group for both the on-therapy and post-therapy therapeutic phases.

SAE, fatal SAE and serious non-fatal AEs will also be summarized following government clinical register format; these summaries will include SAEs of hypoglycemia event.

Summaries and by subject listings of fatal AEs and serious non-fatal AEs will be presented.

8.2.6. Adverse Events Leading to Discontinuation of Investigational Product and/or Withdrawal from the Study

A summary of the number and percentage of subjects with adverse events leading to permanent discontinuation of study treatment from the study will be presented by treatment group for the on-therapy phase.

A summary of the number and percentage of subjects with adverse events leading to withdrawal from the study will be presented for the on-therapy phase.

A by-subject listing of all adverse events leading to permanent discontinuation of study drug/withdrawal from the study will be produced.

8.2.7. Adverse Events of Special Interest

For selected AEs of special interest such as hypoglycemia, the exposure-adjusted event rate, i.e., AE density, will be calculated as the number of events in a given period divided by the total person time on treatment of subjects at risk within the same period; the exposure-adjusted incidence rate will also be calculated as the number of subjects in a given period divided by the total person time on treatment of subjects at risk within the same period. The exposure-adjusted event rate and incidence rate will be expressed as an annualized rate (expected number of events or subjects per 100 person-years).

For any AEs of special interest, summary tables and by subject data listings will be provided.

8.2.7.1. Hypoglycemic Events

Hypoglycemic events merit special attention in the development and study of drugs for the treatment of T2DM since they are often related to the efficacy of a compound. In order to accomplish this, hypoglycemic event data including supplemental hypoglycemic event information not collected on AE eCRF page are reported on a separate hypoglycemic event eCRF page. However, any hypoglycemic event that meets the criteria for a serious AE will also be included in the serious AE summaries.

Analysis of on-therapy hypoglycemic events will include all AEs coded to the preferred term of 'Hypoglycemia'. For on-therapy hypoglycemic events the number and percentage of subjects with events, the number of events, the incidence rate (per 100 person-years) and AE density (per 100 person-years) by the severity of the event defined by American Diabetes Association [ADA], SAE status, relationship to the investigational product, and withdrawal status will be summarized by treatment group. The events will also be summarized according to intervention provided, action taken with regard to background and anti-hyperglycemic medications and onset week and glucose levels. All hypoglycemic events will be classified as severe, documented symptomatic, asymptomatic, probable symptomatic, or pseudohypoglycemia per the American Diabetes Association criteria.

The incidence of hypoglycemia with blood glucose <56 mg/dL (<3.1 mmol/L), regardless of symptoms, will also be summarized by treatment group.

On-therapy hypoglycemic events over time will be summarized by onset week and plotted for each treatment group.

A by-subject listing of all hypoglycemic events will be produced.

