7.4.1.5. AEs of Special Interest

In the Phase IIIa clinical development program, AEs of special interest included several areas of safety related concern for the T2DM population, particularly for a GLP-1R agonist such as albiglutide.

Specific eCRF pages will be used to capture additional details for the following AEs of special interest:

- Hypoglycemic events
- Liver events
- CV events (see Section [7.4.1.4](#))
- Injection site reactions
- Potential systemic allergic reactions
- Pancreatitis
- MTC
- Diabetic retinopathy
- Pneumonia
- Atrial fibrillation/atrial flutter

The following additional AEs of special interest will be captured in the AE eCRF pages:

- GI events
- Pancreatic cancer
- Malignant neoplasms
- Appendicitis

Subjects with drug hypersensitivity reactions that are not reasonably attributable to another cause or pancreatitis should discontinue investigational product and should not be rechallenged with albiglutide (see Section [5.5](#) for complete list of AEs of special interest requiring withdrawal).

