7.4.9. Hypoglycemic Events

Specific criteria for monitoring hypoglycemic events have been designed to ensure subject safety and to closely monitor hypoglycemia. Hypoglycemic events are defined as follows [Seaquist, 2013]:

Severe Hypoglycemia

- Severe hypoglycemia is an event requiring assistance of another person to actively administer carbohydrates, glucagon, or take other corrective actions. Plasma glucose concentrations may not be available during an event, but neurological recovery following the return of plasma glucose to normal is considered sufficient evidence that the event was induced by a low plasma glucose concentration.

Documented Symptomatic Hypoglycemia

- Documented symptomatic hypoglycemia is an event during which typical symptoms of hypoglycemia are accompanied by a measured plasma glucose concentration ≤ 70 mg/dL (≤ 3.9 mmol/L).

Asymptomatic Hypoglycemia

- Asymptomatic hypoglycemia is an event not accompanied by typical symptoms of hypoglycemia but with a measured plasma glucose concentration ≤ 70 mg/dL (≤ 3.9 mmol/L).

Probable Symptomatic Hypoglycemia

- Probable symptomatic hypoglycemia is an event during which symptoms typical of hypoglycemia are not accompanied by a plasma glucose determination but that was presumably caused by a plasma glucose concentration ≤ 70 mg/dL (≤ 3.9 mmol/L).

Pseudohypoglycemia

- Pseudohypoglycemia is an event during which the person with diabetes reports any of the typical symptoms of hypoglycemia with a measured plasma glucose concentration > 70 mg/dL (> 3.9 mmol/L) but approaching that level.

Any hypoglycemic event, regardless of intensity, that satisfies the definition of an SAE ([Appendix 5](#)) should be categorized as outlined in this section and reported appropriately in the SAE eCRF page and the hypoglycemic events AE of special interest page.

7.5. Tracking of Albiglutide Lyophilized DCC Pen Injector and Liquid Auto-injector Failures and User Errors

All albiglutide lyophilized product DCC pen injector and liquid product auto-injector failures and user errors must be detected, documented, and reported by the investigator throughout the study. Detailed information on DCC pen injector and auto-injector failures and user errors will be collected on the Injector Pen and Auto-injector Failure Reporting Form.

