9.4.2. Secondary Analyses

The evaluation of the safety and tolerability as assessed by immunogenicity and ISRs of albiglutide liquid drug product and the lyophilized drug product will be provided by reporting the event rates, and the associated 95% CI.

The overall general safety and tolerability of albiglutide liquid drug product versus lyophilized drug product will be evaluated in tabular and/or graphical format and summarized descriptively.

AEs and SAEs, physical examinations, clinical laboratory evaluations, vital sign measurements, and 12-lead electrocardiogram will be summarized by treatment group. For continuous variables, these summaries will include sample size, mean, median, standard deviation (and/or standard error), minimum, and maximum. For categorical variables, the summaries will include frequencies and corresponding percentages. The exposure-adjusted incidence rate will also be calculated as the number of events in a given period divided by the total person time on treatment of subjects at risk within the same period. The exposure-adjusted incidence rate will be expressed as an annualized rate expected. No inferential testing will be performed on the safety variables. Hypoglycemic events will be analyzed separately from other AEs. All hypoglycemic events will be classified as severe, documented symptomatic, asymptomatic, probable symptomatic, and pseudohypoglycemia, as defined in Section 7.4.9.

AEs will be coded using MedDRA. AEs will be summarized in various subsets, including on therapy AEs, related AEs, AEs leading to treatment discontinuation or withdrawal from study, SAEs, fatal AEs, etc. AEs will also be summarized by maximum intensity (mild, moderate, and severe).

Anti-albiglutide antibody results will be summarized by treatment group. In addition, the number and percentage of subjects with positive results along with the antibody titer values will be provided by visit.

The secondary endpoint FPG change from baseline at Week 26 will be analyzed using MMRM without imputation.

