8.2.4. Adverse Events

All AEs will be coded using MedDRA which will be updated whenever available throughout the life of the study. Adverse events will be categorized by their occurrence in regard to therapeutic phase (pre-therapy, on-therapy, or post-therapy) as defined in [Appendix 4](#). Adverse events will be summarized in various subsets by treatment group. An overview summary of the number and percentage of subjects with any AE, the total number of AEs recorded, and the overall AE density and incidence rate for on-therapy AEs will be provided by treatment group. The overview will also summarize SAEs, treatment-related AEs, AEs by maximum intensity, and AEs by therapy phase.

Summaries of the number and percentage of subjects with any treatment-emergent AEs (TEAEs), related AEs, AEs leading to treatment discontinuation or withdrawal from study, SAEs, fatal AEs, will be provided. Adverse events will also be summarized by maximum intensity (mild, moderate, and severe).

AE summaries will not include hypoglycemic events, unless otherwise specified – The exceptions are summaries for serious AEs, AEs leading to withdrawal from treatment/study and pre-therapy AEs.

All AEs will be listed in a subject data listing.

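### The SAP's only stated rule for the on-therapy hypoglycemia tables is one MedDRA preferred term, while the protocol defines events by assistance, symptoms and glucose, so some qualifying events can be left out

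*SAP*

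**What the plan says.** Protocol 7.4.9 sets out five categories. The first rests on help from another person: "Severe hypoglycemia is an event requiring assistance of another person to actively administer carbohydrates, glucagon, or take other corrective actions". The next two use a measured value at or below 70 mg/dL: "Documented symptomatic hypoglycemia is an event during which typical symptoms of hypoglycemia are accompanied by a measured plasma glucose concentration" and "Asymptomatic hypoglycemia is an event not accompanied by typical symptoms of hypoglycemia but with a measured plasma glucose concentration". Probable symptomatic events have symptoms but no glucose reading. Pseudohypoglycemia has symptoms with a reading above, but close to, 70 mg/dL.

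On capture, Protocol 7.4.1.5 says "Specific eCRF pages will be used to capture additional details for the following AEs of special interest", and hypoglycemic events head that list. On analysis, Protocol 9.4.2 says "Hypoglycemic events will be analyzed separately from other AEs" and commits to placing all of them in the 7.4.9 categories.

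SAP 8.2.7.1 acknowledges that hypoglycemia data "are reported on a separate hypoglycemic event eCRF page". It then describes the analysis: "Analysis of on-therapy hypoglycemic events will include all AEs coded to the preferred term of" *Hypoglycemia*. The same section promises a breakdown by all five categories.

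SAP 8.2.4 adds: "AE summaries will not include hypoglycemic events, unless otherwise specified". Its exceptions are serious AEs, AEs leading to withdrawal from treatment or study, and pre-therapy AEs.

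**The concern.** No category in Protocol 7.4.9 depends on a dictionary term. A preferred term follows from what the site writes on the AE page, so a rule built on one term selects events by wording rather than by the protocol's criteria. An event can satisfy 7.4.9, sit on the dedicated page, and still fail the SAP rule.

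At stake is the completeness of a descriptive safety summary. Hypoglycemia is an identified risk in the protocol's risk table (4.6.1) and an AE of special interest. The arm-level counts and rates are what a reader will use to compare the two products on it. The five-category table is only as complete as the set it is drawn from.

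**Working it through.** The plan gives no expected event rate or coding share, so there is no figure to reproduce. The check compares the case definition with the selection rule.

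**Step 1. Does the rule guarantee that each category is selected?**

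| Category (Protocol 7.4.9) | What qualifies it | How it could miss the SAP rule |
|---|---|---|
| Severe | Assistance; glucose value not essential | Reported by its consequence |
| Documented symptomatic | Symptoms plus value ≤70 mg/dL | Least likely; the diagnosis is evident |
| Asymptomatic | Value ≤70 mg/dL alone | Reported as a low reading, or not recorded as an AE |
| Probable symptomatic | Symptoms, no reading | Reported as symptoms |
| Pseudohypoglycemia | Symptoms, reading >70 mg/dL | Reported as the symptom, since the value is not low |

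The *not recorded as an AE* route comes from Protocol 12.5.1, where abnormal findings count as AEs only if the investigator judges them clinically significant. The SAP rule takes only coded AEs.

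**Step 2. Where would such an event still appear?**
- If serious: in the SAE summaries (SAP 8.2.5 and 8.2.7.1). However, severe in 7.4.9 means assistance, which is not the protocol's definition of serious (12.5.2), so these tables need not catch every severe event.
- If it led to withdrawal, or was pre-therapy: in those summaries (SAP 8.2.4).
- If recorded as an AE: in the listing of all AEs, and possibly in the register-format summaries that include hypoglycemia (SAP 8.2.4.1, 8.2.4.5). Those are not broken down by 7.4.9 category.
- The additional summary of glucose below 56 mg/dL leaves out values from 56 to 70 mg/dL and events with no reading. It may also draw on the same preferred-term set.
- A by-subject listing of all hypoglycemic events is planned, but a listing does not correct arm-level counts.

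**Step 3. How does the SAP treat other events of special interest?** Injection site reactions come from the investigator's eCRF report (8.2.2). Systemic allergic, liver and pneumonia events use the eCRF report plus a customized MedDRA query (8.2.7.6, 8.2.7.7, 8.2.7.9). Appendicitis takes every preferred term containing that word (8.2.7.11). The stated hypoglycemia rule is narrower than all of these.

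**Step 4. Size, by assumption only.** SAP 11.5.4 defines event density as D = E/T, events over person-time. If a share *f* of qualifying events is not selected, the reported density is D′ = (1 − f)E/T, a relative fall of *f*:
- f = 0.05 gives 5% lower
- f = 0.10 gives 10% lower
- f = 0.30 gives 30% lower

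The documents give no value for *f*; this range is illustrative. With the same *f* in both arms, the ratio of densities is unchanged, because (1 − f) cancels. The number of subjects with any event falls only where all of a subject's events are missed.

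**The case against.** The strongest reply is that the SAP sentence says what the analysis will include, not that it includes nothing else. It follows a paragraph placing the data on the dedicated page, and the planned tables by symptom, severity, intervention and glucose level (Tables 3.72 and 3.73) appear to need page data. On that reading the page supplies the set and the preferred-term sentence only adds to it. That is a fair reading, but no page-based rule is written down. If the sentence is not exclusive, nothing states what else comes in, and the set remains undefined.

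Second, Protocol 12.5.4 tells investigators to record a diagnosis rather than signs and symptoms where they can establish one. An investigator completing a hypoglycemia page has already recognised the event as such. This makes miscoding of severe events less likely. It does not settle pseudohypoglycemia, or low readings not reported as AEs.

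Third, coding conventions and page design are not in the documents and might route every page record to this term. Protocol 7.4.1.5 also describes the pages as holding additional details of AEs. If a page opens only from an AE, the *not recorded as an AE* route would be a capture problem rather than a selection problem. These objections limit the point to a possible loss.

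A reader might also infer that a missed event vanishes from both the hypoglycemia tables and the AE reporting. The documents do not support that, given the SAE, withdrawal, pre-therapy and register-format summaries and the listings.

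**Conclusion.** The mismatch stands as a minor analysis-definition gap. The SAP's one stated rule does not guarantee the set that Protocol 9.4.2 commits to classify. Applied literally, it can leave qualifying events out of Tables 3.71 to 3.73 and 3.80, most plausibly asymptomatic and pseudohypoglycemia events.

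The number affected cannot be determined from the documents. A reader might infer a specific undercount, or that a severe event would disappear from the count. Neither follows, because neither an event rate nor a miscoding share is given. Nor is there a stated reason for the effect to differ by arm in a double-blind trial. No inferential testing is planned on safety variables, and the primary HbA1c comparison is untouched.

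The conclusion assumes that the rule is applied as written and that at least some page records can carry another preferred term or lack a coded AE.

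**What to change.** In SAP 8.2.7.1, define the on-therapy analysis set as every record on the hypoglycemic event eCRF page that meets a Protocol 7.4.9 category, plus any AE coded to *Hypoglycemia*. Requiring a 7.4.9 category keeps out page records that meet no protocol definition. Reconcile the two sources, querying mismatches, before database freeze and unblinding.

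Use the same flag for the exclusion in SAP 8.2.4, which does not now say whether the page or the preferred term identifies the excluded events. Keep the SAP's deliberate double reporting in the serious, withdrawal, pre-therapy and register-format summaries.

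The cost is a short SAP edit, one derived flag and minor reconciliation work on data already collected. The reported rate may be slightly higher.
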